## SUMMARY TABLE

Title	A Pilot Study of FDA Approved Optiflow™ THRIVE versus Standard Non-Rebreathers in Patients with Potential High Risk of Airway Obstruction during Total Intravenous Anesthesia Procedures
Project Office	Division of Anesthesiology, Critical care and Pain Management; FC13.2036
Study Size (# of patients)	A proposed sample size of eligible 120 patients (60 patients randomized equally between two groups)
Study Design	This is a prospective randomized trial. All the eligible subjects will be randomly assigned to one of two groups: the Optiflow THRIVE group or the standard non-rebreather group.
Primary Objective	To investigate the performance of Optiflow™ THRIVE relative to Standard Non-Rebreathers in patients with high risk of difficult airway management undergoing total intravenous anesthesia (TIVA) procedures.
Secondary Objective(s)	To describe the episodes of hypoxia (defined by $\text{SpO}_2 \leq 92\%$ ) and the episodes of airway support which include: jaw thrust, chin lift or insertion of an airway supporting device, such as oral/nasal airway or supra airway device in order to recover the level of oxygenation above 92% associated with Optiflow™ THRIVE.
Inclusion Criteria	A patient who meets all the following criteria may be included in the study: 1. 18 years of age and older and signed consent for the study 2. Presents with a $\text{SpO}_2 \geq 95\%$ while breathing room air 3. Requires TIVA but not tracheal intubation during the proposed procedure – PLUS, any of the following: Body mass index (BMI) $\geq 32 \text{ kg/m}^2$ ; neck circumference $\geq 43 \text{ cm}$ in a male and $41 \text{ cm}$ in a female patient; has been diagnosed with moderate to severe obstructive sleep apnea (OSA) by a sleeping study with/without using a continuous airway pressure (CPAP) device; or, full course head and neck radiotherapy $\leq 6$ months (The peak onset time of acute facial and airway edema)
Exclusion Criteria	A patient who meets any of the following will be excluded from the study: 1. Has a significant pulmonary disease requiring supplemental oxygen in daily life (severe pulmonary fibrosis, severe COPD, etc.) 2. Has significant cardiac disease (including history of myocardial infarction (MI) with concurrent evidence of ischemic myocardial damage at the event, cardiomyopathy with impaired left ventricular ejection fraction to less than 50% or uncompensated congestive heart failure (CHF) 3. Cannot tolerate TIVA or having a proposed procedure without TIVA 4. Requires endotracheal intubation 5. American Society of Anesthesiologists (ASA) classification 5 6. Non-English speaking 7. Requires an emergency procedure
Outcome(s)/Endpoint(s)	The primary endpoint is the total length of desaturation episodes (ToLDE) time (in minutes) during a fixed 60-minute observation window during TIVA in patients with high risk of difficult airway management. Desaturation episodes are characterized by the occurrence of hypoxia (defined by $\text{SpO}_2 \leq 92\%$ ).
Study Procedures	
Pretreatment Evaluation	Routine preoperative interview and physical evaluation. No special evaluation required.
On-Study Visits	Onsite data collection in all the study patients including: 1. FDA approved Intervention group: patients receiving Optiflow™ THRIVE 2. Standard of Care group: patients receiving non-rebreather mask  Each patient will be followed for 60 minutes (from induction until 60 minutes thereafter).
Follow-up Visits	Per standard post-anesthesia care unit (PACU) discharge protocol
End of Study Visit	Per standard PACU discharge protocol

Brief Analysis Plan	
For Primary Objective: A total of 120 eligible patients will be randomized in a 1:1 fashion using CORe. Blocking will be utilized to maintain exactly 60 patients per study group. The sample size is used to compensate for cases aborted post-randomization due to interventional radiology procedure changes interfering with the original treatment plan. This strategy will ensure at least 50 patients are randomized and evaluable per study arm. All patient data will be summarized using descriptive statistics. For each study group, the ToLDE time will be summarized using the mean, standard deviation, median, and range. Interval estimation of the difference between study groups in mean ToLDE time will be computed with a 95%CI.
 
With at least 50 patients per group, the precision conferred on the bounds of a two-sided a 95% CI extends 0.39 units on each side of the observed mean assuming a common standard deviation of 1.0 per group (nQuery Advisor v7.0).
 
Descriptive statistics will be used to summarize continuous outcomes, and histograms and scatter plots will be used to explore the distributional characteristics and bivariate relationships, respectively. Transformations to the data will be applied if appropriate. Interval estimates will be computed for continuous variables, such as the mean number of hypoxemia (defined by <math>\text{SpO}_2 \leq 92\%</math>) episodes within the pre-specified time period, for each study group (at least <math>n = 50</math>) independently using a 2-sided 95%. Exploratory analyses between study groups will be conducted using t-tests (Wilcoxon rank-sum tests) for continuous covariates and chi-square tests (Fisher's exact tests) for categorical variables. Linear regression will be used to estimate the mean ToDLE time difference while adjusting for select covariates of interest.

----------------------------	---

## 1. OBJECTIVES

**Primary:** To investigate the performance of Optiflow™ THRIVE relative to Standard Non-Rebreathers in patients with high risk of difficult airway management undergoing total intravenous anesthesia (TIVA), for the planning of future clinical studies.

**Secondary:** To describe the episodes of hypoxia (defined by  $\text{SpO}_2 \leq 92\%$ ) and the episodes of airway support which include: jaw thrust, chin lift or insertion of an airway supporting device, such as oral/nasal airway or supra airway device in order to recover the level of oxygenation above 92% associated with Optiflow™ THRIVE.

## 2. BACKGROUND

Total intravenous anesthesia (TIVA), a general anesthesia technique typically achieved by continuous infusion of propofol with/without adjuvant agents, is commonly used for the diagnostic or brief therapeutic procedures to improve the patient's satisfaction. During TIVA, partial or total airway obstruction resulting in transient oxygen desaturation are the common issues requiring airway support with various maneuvers or use of an artificial device to recover adequate oxygenation. In addition, episodic centrally mediated apnea occurs due to changing in dosing and infusion rate of propofol administration; positive pressure ventilation with facemask may be needed at times. However, when the airway obstruction occurs in a patient with a potential difficult airway such as obstructive sleep apnea (OSA), mass or edema in airway, decreasing or ceasing the oxygen flow delivered to the lungs due to obstruction of flow path quickly results in oxygen desaturation. Managing the airway and re-establishing the oxygen flow to the lungs to maintain the adequate oxygen level in these patients imposes significant challenges to anesthesia providers; prolonged hypoxemia may occur and impose significant adverse influences to the outcomes.

Delivering up to 70 L/min. humidified oxygen flow rate, Optiflow™ THRIVE (Fisher & Paykel Healthcare, Auckland, New Zealand), is proven to provide prolonged duration of apneic oxygenation and quickly restoring the oxygenation saturation to the patient's baseline level when the airway is under control. Due to its high flow rate, the device offers multiple supports to the airway. First, it creates an oxygen-rich environment in the entire airway and reduces the ratio of dead space to tidal volume and therefore, increasing alveolar ventilation. Secondly, it creates a dynamic positive airway pressure to promote slow and deep breathing achieved by decreasing airway resistance during inspiration and prolonging the expiratory phase by a low level of continuous positive airway pressure (CPAP). In addition, it delivers humidified oxygen and improves mucociliary clearance in the airway; therefore, preventing airway mucosa dry-out for a prolonged

application. Thus, Optiflow™ provides ideal airway support during TIVA administration. Although the Optiflow™ has been studied in patients with normal airways, its use in patients with a high risk of airway obstruction during TIVA remains unclear.

TIVA is commonly used in the procedures in interventional radiology and gastrointestinal (GI) endoscopy procedures. At MDACC, challenging airways are often seen in these areas. Obesity, cancer airways, s/p head and neck radiotherapy, etc. increase the risk of difficult airway management; lengthy procedures increase the duration of airway management and the positions for procedures may prevent anesthesia providers to access the airways. Therefore, the patients undergoing these procedures with TIVA present unique chance to investigate the clinical feasibility of improving the airway safety by using Optiflow THRIVE to manage the case in high airway risk patients.

This study will assist with establishing the hypothesis that can be objectively assessed if an airway managed with Optiflow™ THRIVE will reduce the risk of intraoperative hypoxia in patients undergoing interventional radiology and GI procedures requiring total intravenous anesthesia (TIVA) by providing knowledge of study endpoints that reflect clinically viable differences. Moreover, we can better understand if Optiflow™ THRIVE assists with the need to provide manual rescue airway techniques (to maintain airway patency) while also decreasing the duration and episodes of hypoxia in patients undergoing the procedures requiring TIVA.

### 3. STUDY DESIGN DESCRIPTION

This is a prospective randomized controlled study. Patients will be randomized in a 1:1 fashion to one of two study groups, the treatment group or control group. The patients in the treatment group will receive oxygen via Optiflow™ THRIVE; while the patients in the control group will receive 100% oxygen via a non-rebreather facemask. CORe will be used to conduct the randomization, as well as random block sizes; recommending to CORe that block sizes of 2, 4, 6, and 8 are allowable. Blocking will be utilized to maintain exactly 50 patients per study group. Patient randomization will occur after a patient has been deemed eligible and consented to participate. The data below listed will be collected during the procedure and statistically compared between the two groups at the end of the study.

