### 4. DISCUSSION OF SUBJECT POPULATION

#### 4.1 Subject Characteristics

- a) **Total number of subjects:** Due to lack of existing data to support a power analysis, the estimated number of study subjects is currently 120 eligible patients with 60 in each group. Due largely to the variation of caseload daily in IR, the average caseload for the study is expected no more than 2 cases/day. With the safety profiles in the previous reports mentioned above, the failure rate or the subject withdraw from the study is estimated no more than 1%.

All included cases will be scheduled elective procedures. Although we expect the rate of patient withdrawal to be low, we will not replace missing slots in the randomization list with the next eligible patient. Those patients will be considered randomized, but unevaluable. If needed, a protocol amendment will take place to increase the total number of randomized patients, only if this turns out to be an issue.

- b) **Study subjects:** Optiflow™ is a standard airway device used routinely and internationally, for high flow nasal oxygen (HFNO) delivery. Multiple studies have demonstrated that Optiflow™ is superior to the existing comparable devices in terms of both oxygenation and CO2 clearance. In addition, its safety profile in maintaining a patent airway is also superior to comparable devices during deep

sedation or general anesthesia (GA) without tracheal intubation. Standard anesthetic care will be provided to all patients with the exception of whether the patients receive HFNO or oxygen via non-rebreather face mask. Thus far, the literature has not demonstrated use in the pediatric population; patients < 18 years of age will not be included in this trial.

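### Section 3 sets the blocking target at 50 per group, but the Summary and Section 6.1 set it at 60 and the stated total is 120

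*Combined protocol and SAP*

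**What the plan says.** Section 3 (Study Design Description) sets 1:1 allocation through CORe, allows random block sizes of 2, 4, 6 and 8, and then states: "Blocking will be utilized to maintain exactly 50 patients per study group".

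The Summary Table's Brief Analysis Plan has the same sentence with a different number: "Blocking will be utilized to maintain exactly 60 patients per study group". Section 6.1 repeats that version. Both places say that 120 eligible patients will be randomised and explain why: the surplus covers cases aborted after randomisation because the interventional radiology procedure changes. The Summary concludes: "This strategy will ensure at least 50 patients are randomized and evaluable per study arm". Section 6.1 says the same in almost the same words.

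The total is also given in two other places. The Study Size row of the Summary has "A proposed sample size of eligible 120 patients", and Section 4.1 says "the estimated number of study subjects is currently 120 eligible patients with 60 in each group".

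On losses, Section 4.1 says that "we will not replace missing slots in the randomization list with the next eligible patient" and adds: "Those patients will be considered randomized, but unevaluable". If this becomes a problem, it foresees a protocol amendment to raise the number randomised.

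The precision statement, in the Summary and Section 6.1, is made for at least 50 patients per group. It says the two-sided 95% interval "extends 0.39 units on each side of the observed mean assuming a common standard deviation of 1.0 per group".

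**The concern.** The protocol gives two different exact values for one design parameter, the number assigned to each group. The outlying value sits directly after the only block-size instructions in the document, so whoever builds the CORe list could reasonably take it from there.

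A list closed at 50 per group would remove the allowance that Section 6.1 describes. Since lost slots are not refilled, any loss in a group would leave it with fewer than 50 evaluable patients. That would break the assurance of at least 50 evaluable per group, on which the stated half-width of 0.39 rests, and could lead to the amendment that Section 4.1 foresees.

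**Working it through.** **Inputs**
- Blocking target per group: 50 (Section 3); 60 (Summary, Brief Analysis Plan; Section 6.1).
- Total randomised: 120 (Summary; Sections 4.1 and 6.1).
- Allocation: 1:1 (Sections 3 and 6.1).
- Minimum evaluable: 50 per group (Summary; Section 6.1).
- Replacement of lost slots: none (Section 4.1).
- Failure or withdrawal: no more than 1% (Section 4.1). No rate is given for aborted cases.
- SD 1.0 per group, two-sided 95% interval (Summary; Section 6.1).

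**Step 1: which target gives the stated total**
- 2 × 60 = 120, which agrees.
- 2 × 50 = 100, which is 20 patients, or 20/120 = 16.7%, too few.

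**Step 2: the plan's own precision figure**

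The half-width for a difference in two means with n per group is 1.96 × SD × √(2/n).
- n = 50: 1.96 × √(2/50) = 0.392. This reproduces the plan's 0.39. The t-based value (98 df) is 0.397.
- n = 60: 1.96 × √(2/60) = 0.358.

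The 0.39 therefore belongs to 50 evaluable per group, with 60 as the number randomised. The allowance is 10 of 60, or 16.7% per group.

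**Step 3: effect of a list of 50**

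| Loss per group | List of 50: n left, half-width | List of 60: n left, half-width |
|---|---|---|
| 1% (upper figure in Section 4.1) | 49.5, 0.394 | 59.4, 0.360 |
| 16.7% (illustration) | 41.7, 0.429 | 50, 0.392 |

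The 16.7% is the largest loss a list of 60 can bear and still keep 50. It is not a rate that the protocol expects. Rounding 41.7 up to 42 patients gives 0.428.

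At any common loss rate the ratio of the two half-widths is √(60/50) = 1.095, so the list of 50 gives an interval 9.5% wider.

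**Step 4: could Section 3's 50 mean evaluable patients?**

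No. Blocking fixes how many are assigned and cannot hold the evaluable number at an exact value. Elsewhere in the protocol, 50 appears only as a minimum (Summary; Sections 6.1 and 6.2). Section 3's sentence also matches the one that says 60, word for word apart from the number.

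**Side check: the label on 0.39**

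The Summary and Section 6.1 place 0.39 around the observed mean. For one group's mean with n = 50 the half-width is 1.96/√50 = 0.277 (t-based, 49 df: 0.284). The figure is for the difference in means.

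**The case against.** The best case on the other side concerns weight, not fact. The documents point clearly to 60: the sample-size section gives the total, the number per group and the reason for the surplus, and the Summary and Section 4.1 support it. One sentence in a design overview disagrees, and a careful reader would work out the intent. The harm arises only if the CORe list followed Section 3, which the documents do not show. The only loss rate they give is at most 1%, and at that rate a list of 50 gives 0.394, which still rounds to the planned 0.39. The trial is a pilot with no power claim, and Section 4.1 already provides for an amendment if numbers fall short.

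Most of this is fair, and it limits the size of the point. Two things remain. The 1% covers failure or withdrawal, whereas the surplus is for aborted cases, whose rate is not given, so the 1% row does not bound the loss. And Section 3 is where the block sizes are specified, so the conflicting number stands in a natural source for the list.

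The label on 0.39 is a separate and minor matter. The sentence before it names the difference between groups, so the intent can be inferred.

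**Conclusion.** The contradiction is real and should be corrected. Section 3 is the only one of three statements of the blocking target that gives 50, and it cannot be reconciled with 120 patients randomised 1:1.

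The consequence is modest: some precision is lost if the list was built to 50 per group, and nothing is lost if it was built to 60. Relative to a list of 60, the interval would be 9.5% wider at any common loss rate. Relative to the planned half-width of 0.392, it would be 0.394 at 1% loss and about 0.43 at 16.7%. These figures assume SD 1.0, the normal formula and equal loss in both groups. The 16.7% is an illustration.

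**What to change.** 1. Check the CORe list first. It should have 120 slots and close at 60 per group. If it was built to 100, bring it up to the 120 that the protocol already states and document the change.
2. In Section 3, replace 50 with 60 in the blocking sentence and add the total of 120.
3. Minor: in the Summary and Section 6.1, say that the 0.39 lies on each side of the observed difference in mean ToLDE time. The sentence already gives the SD of 1.0, so the units need no further wording.

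The cost is one number, one check of the list and one label in two places. The planned total, the analysis and the 0.39 calculation stay as they are. If the list turns out to have 100 slots, extending it is an added task.

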### 4. DISCUSSION OF SUBJECT POPULATION

#### 4.1 Subject Characteristics

- a) **Total number of subjects:** Due to lack of existing data to support a power analysis, the estimated number of study subjects is currently 120 eligible patients with 60 in each group. Due largely to the variation of caseload daily in IR, the average caseload for the study is expected no more than 2 cases/day. With the safety profiles in the previous reports mentioned above, the failure rate or the subject withdraw from the study is estimated no more than 1%.

All included cases will be scheduled elective procedures. Although we expect the rate of patient withdrawal to be low, we will not replace missing slots in the randomization list with the next eligible patient. Those patients will be considered randomized, but unevaluable. If needed, a protocol amendment will take place to increase the total number of randomized patients, only if this turns out to be an issue.

- b) **Study subjects:** Optiflow™ is a standard airway device used routinely and internationally, for high flow nasal oxygen (HFNO) delivery. Multiple studies have demonstrated that Optiflow™ is superior to the existing comparable devices in terms of both oxygenation and CO2 clearance. In addition, its safety profile in maintaining a patent airway is also superior to comparable devices during deep

sedation or general anesthesia (GA) without tracheal intubation. Standard anesthetic care will be provided to all patients with the exception of whether the patients receive HFNO or oxygen via non-rebreather face mask. Thus far, the literature has not demonstrated use in the pediatric population; patients < 18 years of age will not be included in this trial.

## 2. Inclusion and Exclusion Criteria

**a) Inclusion Criteria:** An individual that meets all of the following will be eligible/considered for the study:

- 1) 18 years of age and older and signed consent for the study.
- 2) Patients with an  $\text{SpO}_2 \geq 95\%$  while breathing room air
- 3) Patients requiring TIVA, but not tracheal intubation during the proposed procedure - PLUS, any of the following criteria:
  - Body mass index (BMI)  $\geq 32 \text{ kg/m}^2$
  - Or, neck circumference  $\geq 43 \text{ cm}$  in a male and  $41 \text{ cm}$  in a female
  - Or, has been diagnosed with moderate to severe obstructive sleep apnea (OSA) with/without using a CPAP device
  - Or, full course head and neck radiotherapy  $\leq 6$  months (The peak onset time of acute facial and airway edema)

**b) Exclusion Criteria:** An individual that meets any of the following will not be eligible/considered for the study:

- 1) Significant pulmonary disease requiring supplemental oxygen in daily life (severe pulmonary fibrosis, severe chronic obstructive pulmonary disease, etc.)
- 2) Significant cardiac disease (including history of MI with concurrent evidence of ischemic myocardial damage at the event, cardiomyopathy with impaired left ventricular ejection fraction to less than 50% or uncompensated congestive heart failure)
- 3) TIVA is contraindicate or having a proposed procedure without TIVA
- 4) Endotracheal intubation is required
- 5) ASA Physical Status classification 5
- 6) Patients who are non-English speaking
- 7) Emergency procedures

## 5. SUBJECT IDENTIFICATION, RECRUITMENT AND CONSENT

### 5.1 Method of Subject Identification and Recruitment

All study investigators, including the Principal Investigator (PI), Co-Investigators (Co-I) and/or collaborators of the study, are eligible for the identification of study candidates. The IR procedure daily schedule will be used for patient selection. Once eligibility of a study candidate has been identified, the study coordinator will be informed to start the patient interview and obtain written informed consent.

### 5.2 Consent Process

The study coordinator will be responsible for the study candidate interview and consenting. Informed written consent will be obtained either electronically or by paper. All signed study consents will be stored in locked file storage or a MDACC encrypted/passcode secured electronic device for any electronic scanned document.

The study device is a standard airway tool that has been used in clinical routine practice for over a period of 10 years with no significant risk or complication for its clinical applications reported in the literature; In fact, its excellent safety profile may be of benefit, especially to those who have obstructive airway disease. In this study, standard application of 100% oxygen administration via non-breather facemask will be compared to administration of HFNO via Optiflow™. A structured informed consent for the study with information mentioned above will be discussed with study candidate and signed by this individual.

